2 STUDY SYNOPSIS

Title	Belzutifan special drug use results survey in radically unresectable or metastatic renal cell carcinoma: a post-authorization safety study (PASS)
Product information	
Therapeutic Category
 
Anticancer drug - Hypoxia-inducible factor 2α inhibitor
 
Active substance
 
belzutifan
 
Brand name
 
WELIREG[®] Tablets 40 mg

Milestones	
Anticipated timeframes for the following major milestones are as follows:
 
Study period
 
MAR 2026 – FEB 2031 (60 months)
 
Registration period
 
APR 2026 – MAR 2029 (36 months)
 
Registration may be discontinued when the target number of cases is reached.
 
Data analysis start
 
MAR 2031
 
Final report
 
MAY 2032 (There are no planned interim reports.)

Rationale and background	
The purpose of this PASS is to comprehensively collect and verify safety information under actual use conditions in domestic subjects based on Japan's GPSP regulations, and to conduct a descriptive investigation. This PASS is being conducted as an additional safety monitoring activity described in the Japanese risk management plan for belzutifan.

Safety Concerns as delineated in the J-RMP for this study
	
Important Identified Risks Anemia and hypoxia
 
Important Potential Risks Hemorrhage and fractures
 
Important Missing Information NA

Objective
	
Among Japanese subjects with radically unresectable or metastatic RCC treated with belzutifan in routine practice,
 
Primary Objective
 
1) To monitor the risk of occurrence of hemorrhages and fractures during the administration of belzutifan in subjects with RCC. In doing so, we will observe the percentage of subjects occurring hemorrhage and fractures during the administration of belzutifan and contrasted the results obtained in this study with the percentage of subjects occurring the relevant AEs observed in the Everolimus group of the Study 005.
 
Secondary Objective
 
1) The overall safety of belzutifan, including safety concerns in subjects with RCC
 
2) The effectiveness of belzutifan in subjects with RCC

Study design
	
Special Survey
 
This study is a non-interventional, descriptive, longitudinal, multi-center collaborative survey.


Study subjects
	
Subjects in Japan with RCC (not Von Hippel-Lindau disease (VHL)-associated) who have received belzutifan in routine clinical practice for the first time as indicated by the current local label.

Planned subject number
	
403 subjects (safety analysis set)

Study method
	
The study will be conducted with the use of EDC system by means of a central registration method. At each site, subjects that meet the inclusion/exclusion criteria will be approached for informed consent. Subjects may be prospectively identified and registered/enrolled at the time of treatment initiation or retrospectively identified and registered/enrolled after treatment initiation but before the end of the registration period.

Endpoint and its measurement
	
Safety endpoints will include investigator reported adverse events, summarized by frequency and severity, and for secondary effectiveness endpoints, response to treatment by local investigator assessment.

Data Analysis
	
Study endpoints will be analyzed using descriptive statistical methods such as mean, standard deviation, median, interquartile range, and/or minimum/maximum/range for continuous variables. For any categorical variables, e.g., AE analysis, frequency and percentage will be reported. There is no hypothesis testing.
 
To assess whether demographic and/or clinical characteristics impact safety endpoints, these characteristics will be analyzed using descriptive statistical methods and reported for all registered subjects, the safety evaluation group, and presence/absence of AEs/select protocol-specified AEs.
 
Details of the statistical analysis will be specified separately in the statistical analysis plan.

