6.5.4 Subject observation

The treatment period is defined as the period from the start date of belzutifan administration until the date of the last administration. The observation period is defined as 12 months (52 weeks) from the start date of the administration. Adverse events will be collected throughout the treatment period and for 30 days following discontinuation of belzutifan treatment. However, the total follow-up period will not exceed the observation period [1 year (52weeks) from the first belzutifan treatment date].

Rationale for the observation period

In the 005 study, the median time to the first occurrence of hemorrhage was 84 days (range: 2 to 728 days), and the median time to the first occurrence of fractures was 277.5 days (range: 5 to 639 days). Additionally, most of the adverse events considered for safety concerns in this survey occurred within three months of the start of administration. To confirm the occurrence status (incidence rate, severity, treatment details, etc.) of these events, a 12-month (52-week) observation period was set.

¹ Any number or symbol that allows the investigator to identify the patient (no patient information such as medical record number required)

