Adverse events will be collected throughout the treatment period and for 30 days following discontinuation of belzutifan treatment. The follow up period for each subject will vary according to the treatment of belzutifan, but the maximum follow-up period will not exceed the observation period [12 months (52weeks) from the first date of belzutifan treatment.]

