6.9.1 Subject composition

Subject attrition will be reported, including:

- Number of the registered subjects
- Number of the subjects for whom the study form has been collected
- Number of the subjects for whom the study form has been finalized (Number of subjects whom the survey form has been quality checked per 6.5.8)

- Number of the subjects included in safety tabulation/subjects excluded from the tabulation and the reason

The subjects that meet the criteria for safety analysis, are treated with belzutifan at least once, complete at least one follow up visit (e.g., re-visit etc.), and are identified by an investigator whether AE occurred or not will be included in the subjects for the safety evaluation. The ‘safety tabulation’ group will be used for all analyses below unless otherwise noted.

- Number of the subjects included in effectiveness evaluation/subjects excluded from the evaluation and the reason

Only subjects in which a) belzutifan was administered at the recommended dose throughout the observation period or until belzutifan discontinuation and b) have an effectiveness evaluation will be included in the effectiveness analyses.

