6.9.3 Secondary Objective analysis

- 1) Patient demographic and clinical characteristics will be analyzed and reported as noted above according to whether they are a categorical or continuous variables for:

- a) the registered subjects
- b) the safety evaluation group
- c) by presence/absence of any adverse event
- d) by presence/absence of hemorrhage
- e) by presence/absence of fracture
- f) by presence/absence of anemia
- g) by presence/absence of hypoxia
- h) by presence/absence of intracranial lesions

- 2) The incidence of anemia AEs and the incidence hypoxia AEs, including all AEs, ADRs, grade 3-5 AEs, grade 3-5 ADRs, SAEs, and SADR will be separately analyzed and reported as categorical variables

- 3) The incidence of intracranial hemorrhage AEs with or without pre-existing intracranial lesions, including all AEs, ADRs, grade 3-5 AEs, grade 3-5 ADRs, SAEs, and SADR reported by the investigator will be separately analyzed and reported as categorical variables
- 4) The incidence of overall safety events reported by investigator, including all AEs, ADRs, grade 3-5 AEs, grade 3-5 ADRs, SAEs, SADR, unexpected SAEs, and unexpected SADR, will be analyzed and reported as categorical variables
- 5) The following will be analyzed and reported as categorical variables for a) hemorrhage AEs, b) fracture AEs, c) anemia AEs, d) hypoxia AEs, e) all AEs, f) all SAEs, g) all ADRs and h) all SADR reported by the investigator:
 - the proportion of subjects who interrupt drug due and the reasons for drug interruption
 - the proportion of subjects who discontinue drug and the reasons for drug discontinuation
 - the proportion of subjects with dose reduction and the reasons for dose reduction
- 6) The following will be analyzed and reported as categorical variables for the effectiveness analysis population based on the investigator's overall assessment after completion of administration, as detailed in the stand-alone statistical analysis plan:
 - ORR: best overall response rate (CR or PR)
 - DCR: best response rate of (CR, PR, SD)

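### Presence/absence tables meant to show whether baseline characteristics affect safety mix risk with length of AE observation, because AE collection stops 30 days after belzutifan stops

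*Protocol*

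**What the plan says.** The Data Analysis entry in section 2 (Study Synopsis) states purpose and method together: "To assess whether demographic and/or clinical characteristics impact safety endpoints, these characteristics will be analyzed using descriptive statistical methods", and these are to be "reported for all registered subjects, the safety evaluation group, and presence/absence of AEs/select protocol-specified AEs". Sections 5.2(a) and 6.9.3 item 1 list the splits: any AE, hemorrhage ("by presence/absence of hemorrhage"), fracture, anemia and hypoxia, plus intracranial lesions.

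Section 6.5.4 sets the AE window: "Adverse events will be collected throughout the treatment period and for 30 days following discontinuation of belzutifan treatment", with the cap that "the total follow-up period will not exceed the observation period [1 year (52weeks) from the first belzutifan treatment date". Section 6.7.3 repeats the window and adds: "The follow up period for each subject will vary according to the treatment of belzutifan".

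Under 6.9.1, subjects enter the safety set if they meet the criteria, "are treated with belzutifan at least once, complete at least one follow up visit", and have known AE status. No minimum duration applies.

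On timing in Study 005, 6.5.4 gives a median of 84 days to first hemorrhage, says that "the median time to the first occurrence of fractures was 277.5 days (range: 5 to 639 days"), and adds that most AEs behind the safety concerns came within three months.

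Section 6.10 lists selection bias, information bias, the lack of an internal comparator and the inability to control for confounders. It does not mention unequal AE observation time.

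**The concern.** The column without the event mixes subjects followed event-free for a year with subjects whose AE collection closed after a few weeks. At the same event hazard, shorter treatment means a shorter window and fewer recorded events. The survey collects features that could plausibly go with shorter treatment in advanced RCC, such as IMDC risk, KPS/ECOG and treatment line (6.6). That link is an assumption; the protocol does not state it. Such a feature would appear less often among subjects with the event, even if it has no effect on risk.

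As a description of who had a recorded event on treatment, the tables are sound. The difficulty is that the synopsis asks them to show whether characteristics affect safety. Section 3 says the results feed a review of the Japanese risk management plan, so a misleading picture of who is at risk could carry forward. This comparison lies inside the survey and is separate from the contrast with the everolimus group.

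**Working it through.** **The plan's own figure.** Section 6.3 asks for a probability above 90% of at least 11 Grade 3 or higher hemorrhages at 3.8%. P(Bin(403, 0.038) ≥ 11) = 0.9005, and 403 is the smallest n that reaches 0.90, so the figure reproduces. It does not bear on this point, but 6.3 also supplies the incidences used below.

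**Inputs from the protocol.** AE window W = min(T + 30, 364) days, where T is time on drug (6.5.4). Hemorrhage 47/372 = 12.6% and fracture 18/372 = 4.8% (6.3).

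**Assumed, because the protocol gives none.** Exponential time on drug; half the cohort has the characteristic; the hazard is identical with and without it (true ratio 1.0), either constant or 3 or 10 times higher in the first 90 days.

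**One case in full.** With mean time on drug m, λ = 1/m and constant hazard h, recorded risk = 1 − [e^(−30h) · λ/(λ+h) · (1 − e^(−334(λ+h))) + e^(−364h) · e^(−334λ)]. Take h = 0.0006/day:
- m = 90: 1 − (0.9132 + 0.0197) = 6.7%, mean window 118 days.
- m = 300: 1 − (0.6086 + 0.2640) = 12.7%, mean window 231 days.
- Crude ratio 0.067/0.127 = 0.53, where the truth is 1.0.

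Keeping these durations and the 12.7% incidence in the longer-treated group, the ratio is 0.68 with a 3-fold early hazard and 0.80 with a 10-fold one.

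**Range, with the hazard calibrated to the Study 005 incidences.** Crude risk ratio, shorter-treated over longer-treated, true ratio 1.0:

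| Median days on drug | Hemorrhage: constant / 3-fold / 10-fold | Fracture: constant / 3-fold / 10-fold |
|---|---|---|
| 365 vs 90 | 0.56 / 0.69 / 0.82 | 0.55 / 0.68 / 0.81 |
| 240 vs 120 | 0.74 / 0.83 / 0.90 | 0.73 / 0.82 / 0.90 |
| 300 vs 60 | 0.46 / 0.62 / 0.76 | 0.45 / 0.61 / 0.75 |
| 180 vs 90 | 0.70 / 0.81 / 0.89 | 0.69 / 0.80 / 0.88 |

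At a given hazard shape the two events behave alike. Fracture is more exposed because its median onset of 277.5 days makes the front-loaded, milder columns less plausible for it.

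In table terms, at 300 vs 60 days with a constant hemorrhage hazard, a characteristic held by 50% of the cohort makes up 31.5% of the presence column and 52.7% of the absence column.

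**A truly harmful characteristic** (hazard ratio 1.5, constant hazard, hemorrhage): the crude ratio is 1.07 at 240 vs 120 days and 0.67 at 300 vs 60 days.

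**Where the early stoppers sit.** Share stopping before day 90, assumed median treatment 180 days, about 29% overall:

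| Event | Constant hazard: absence / presence | 10-fold early hazard: absence / presence |
|---|---|---|
| Hemorrhage | 32% / 10% | 31% / 21% |
| Fracture | 30% / 10% | 30% / 21% |
| Hypoxia | 32% / 10% | 31% / 21% |
| Anemia | 75% / 20% | 49% / 25% |

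The anemia row uses about 83%, the rate at which P(Bin(403, p) ≥ 325) reaches 0.90 (6.3). That leaves about 403 × 0.17 ≈ 69 subjects without anemia. If half of on-treatment hemorrhages themselves end treatment (constant hazard), the hemorrhage row narrows to 32% / 26%.

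**Check on the remedy.** A single person-year rate does not solve this. At means of 90 and 300 days with a true ratio of 1.0, the rate ratio is 1.00 under a constant hazard but 1.29 with a 3-fold and 1.53 with a 10-fold early hazard, because short-stayers contribute mostly high-hazard time.

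**The case against.** The survey is descriptive throughout. The synopsis rules out hypothesis testing, 5.2(a) asks only for a description of characteristics, the causal-sounding verb appears only in the synopsis, and 6.10 asks for cautious reading. Table detail belongs to the statistical analysis plan, which is not at hand. Most events come early, which shrinks the bias, and no document says that any characteristic shortens treatment.

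Much of this stands. The absence of exposure-adjusted tables from the protocol is not the finding, since the analysis plan may contain them. What remains is protocol text: a stated purpose that the fixed comparison cannot serve, and a limitation that 6.10 leaves out. Leaving out tests does not remove a bias in the percentages.

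Two stronger readings are tempting, and neither is supported. A reader might infer that every event-free column fills with early stoppers. That fits anemia and, by the same reasoning, any AE, where few subjects are event-free. For hemorrhage, fracture and hypoxia the absence column stays within about 4 points of the cohort, and early stoppers are mainly missing from the presence column. A reader might also infer that any characteristic shortening treatment will look protective. That is a tendency: at 240 vs 120 days a hazard ratio of 1.5 is masked (1.07), not reversed. AE-driven stopping narrows the contrast further.

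**Conclusion.** The point holds in limited form. The presence/absence tables describe on-treatment events validly, but they cannot show whether characteristics affect safety, because the groups differ in how long AEs were collected and the protocol does not say so. The direction follows from the AE window: at equal hazard, shorter treatment gives fewer recorded events.

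The size cannot be derived from the documents. Over the assumed durations and hazard shapes, a characteristic with no effect shows a crude risk ratio of about 0.45 to 0.90. The upper end applies when events are concentrated early and durations differ moderately; the lower end when the hazard is flat and durations differ widely. This warrants a change to the protocol text and a few added summaries. It does not threaten the primary description of hemorrhage and fracture incidence during treatment.

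**What to change.** - **6.9.3 item 1:** keep the tables and add treatment duration and AE-observation time to each AE presence/absence column.
- **6.9.3:** for hemorrhage, fracture, anemia and hypoxia, add a descriptive time-to-first-event summary by a few main baseline factors already collected, for example IMDC risk, performance status and treatment line. Use cumulative incidence censored at the end of each subject's AE window, or rates split by time since start (for example at 90 days). Do not rely on one overall person-year rate. State that the summary assumes subjects whose window has closed would have had the same later risk as those still observed.
- **Section 2, Data Analysis:** replace the wording about impact with a descriptive association between characteristics and recorded AEs.
- **6.10:** name unequal AE observation time, and its likely direction, as a limitation.

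The cost is wording plus a few descriptive tables. Belzutifan start and stop dates and AE onset dates are already collected (6.6), so no extra data or subjects are needed. Fracture cells will be sparse: about 0.048 × 403 ≈ 19 expected events, which is a reason to keep the list of factors short.

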3 MILESTONE

Milestone	Planned Date or Description
Study period	MAR 2026 to FEB 2031 (60 months)
Enrollment and follow-up period	APR 2026 to MAR 2029 (36 months) Registration may be discontinued when the target number of cases is reached. Subjects will be followed up to 12 months after treatment initiation.
J-PSUR	Safety information will be reviewed comprehensively at the time of J-PSUR reporting.
Data analysis start	MAR 2031
Final report submission to Japan PMDA	MAY 2032
Milestones for evaluation and reporting, and possible further measures based on the results of the study	Based on the results of this study, the Japanese risk management plan will be reviewed and a recommendation will be made as to whether or not changes are required.

4 RATIONALE AND BACKGROUND

The purpose of this Study is to collect/ascertain more completely the number of AEs in the local population, and describe the AEs in the local population according to the local regulation.

This study is conducted as part of the pharmacovigilance plan proposed by the Japanese Risk Management Plan (J-RMP) for belzutifan. The safety concerns as delineated in the J-RMP for this study are:

- 1) Important Identified Risks
Anemia and hypoxia
- 2) Important Potential Risks
Hemorrhage and fractures
- 3) Important Missing Information
NA

5 OBJECTIVES

5.1 Primary Objective

- 1) To monitor the risk of occurrence of hemorrhages and fractures during the administration of belzutifan in subjects with RCC. In doing so, we will observe the percentage of subjects occurring hemorrhage and fractures during the administration of belzutifan, and contrasted the results obtained in this study with the percentage of subjects occurring the AEs observed in the everolimus group of the Study 005.

To address the Primary Objective, the incidence of hemorrhage AEs and the incidence of fracture AEs, including all adverse events (AEs), adverse drug reactions (ADRs), grade 3-5 AEs, grade 3-5 ADRs, serious AEs (SAEs), and serious ADRs (SADR) will be described.

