6.9.2 Primary Objective analysis

The incidence of hemorrhage AEs and the incidence fracture AEs reported by investigator, including all AEs, ADRs, grade 3-5 AEs, grade 3-5 ADRs, SAEs, and SADR will be analyzed and reported as categorical variables.

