6.9.4 Exploratory analysis

For all Primary objectives noted within, the results of this survey, as well as results from other relevant, published studies (LS005 etc.) will be qualitatively compared and reported. In addition to noting any similarities/differences in observed trends, any differences between this study and other relevant, published studies (LS005 etc.), including methodologies or study population, will be reported, as will any other limitations that may impede assessment of comparability. Given the inherent limitations associated with cross-study comparisons—such as differences in study design, patient demographics, and assessment methodologies—no formal statistical testing will be conducted. These analyses are intended to provide contextual understanding of the safety profile of belzutifan and are not designed to support formal statistical inference.

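### The primary contrast with the Study 005 everolimus arm compares crude percentages over unmatched observation times, and the primary analysis section does not contain it

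*Protocol*

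**What the plan says.** - **Objective.** Section 5.1 (repeated in the synopsis and in Part B) states that "we will observe the percentage of subjects occurring hemorrhage and fractures during the administration of belzutifan", to be contrasted with the "percentage of subjects occurring the AEs observed in the everolimus group of the Study 005". The measure on both sides is a percentage of subjects.
- **Primary analysis.** Section 6.9.2 covers hemorrhage and fracture AEs, ADRs, grade 3-5 events, "SAEs, and SADR will be analyzed and reported as categorical variables". It does not mention the contrast.
- **Where the contrast appears.** Section 6.9.4, headed exploratory, says that the survey results and those of "other relevant, published studies (LS005 etc.) will be qualitatively compared and reported". The everolimus arm is not named there.
- **Survey window.** Section 6.5.4: "The observation period is defined as 12 months (52 weeks) from the start date of the administration". Section 6.7.3 collects adverse events on treatment and for 30 days afterwards, within that cap, and says "The follow up period for each subject will vary according to the treatment of belzutifan".
- **Study 005 timing.** Section 6.5.4: "the median time to the first occurrence of hemorrhage was 84 days (range: 2 to 728 days"). For fracture it gives a median of 277.5 days and a range of 5 to 639 days.
- **Limits on the comparison.** Section 6.9.4 makes it qualitative and untested, with differences in methodology and population to be reported. Section 6.10 says the results cannot be statistically compared with earlier trials. Neither names length of follow-up or exposure.

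**The concern.** A crude percentage of subjects with an event depends on the hazard and on how long subjects are watched. Here the survey's watching time is capped at 52 weeks and ends 30 days after the drug stops, while the reference percentage comes from a trial in which first events were still being recorded well into the second year. If the hazards were identical, the two percentages could still differ. If the hazards differed, unequal exposure could hide it.

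This contrast is written into the primary objective, for two important potential risks in the Japanese risk management plan. A reader of the final report will see two percentages side by side and read the gap as information about the drug. Because 6.9.2 does not carry the contrast and 6.9.4 broadens the comparator, the report would also have no fixed primary presentation of it.

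**Working it through.** **Inputs**
- Study 005: hemorrhage 47/372, fracture 18/372 (6.3).
- First-onset times: hemorrhage median 84 days, maximum 728; fracture median 277.5 days, maximum 639 (6.5.4).
- Survey cap: 52 weeks = 364 days (6.5.4, 6.7.3). N = 403 (6.3).
- Not in the document: the everolimus percentage, exposure and onset times, and the AE collection window used in Study 005.

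**Assumption.** Neither section labels these figures by arm. Section 6.3 uses the 372-subject figures to project belzutifan counts. Below, the onset times are taken to belong to those same 372 subjects.

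**Step 1. The plan's own figures.** 47/372 = 12.6% and 18/372 = 4.8%, as stated. The sample size also reproduces: with X binomial (403, 0.038), P(X ≥ 11) = 0.9005, and 403 is the smallest n that reaches 90%.

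**Step 2. What a 364-day cap could remove.** The median and maximum bound the number of late first events without any assumption about the shape of the distribution.
- Fracture (18 events): the maximum of 639 means at least 1 falls after day 364. The median of 277.5 means at least 9 fall by then, so at most 9 are late. Capped percentage: (18 − 9)/372 = 2.4% to (18 − 1)/372 = 4.6%.
- Hemorrhage (47 events): the maximum of 728 means at least 1 is late. The 24th ordered event is at day 84, so at most 23 are late. Capped percentage: (47 − 23)/372 = 6.5% to (47 − 1)/372 = 12.4%.

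| Event | Full figure | Capped at 52 weeks | Loss (points) | 95% half-width at N=403 |
|---|---|---|---|---|
| Fracture | 4.8% | 2.4-4.6% | 0.3-2.4 | 2.1 |
| Hemorrhage | 12.6% | 6.5-12.4% | 0.3-6.2 | 3.2 |

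Half-width = 1.96 × √(p(1 − p)/403), with p = 18/372 and 47/372. The upper end of each loss exceeds sampling error; the lower end is negligible.

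**Step 3. Why the direction is open.** Take an identical constant hazard on both sides and let survey exposure be a multiple k of reference exposure. A reference percentage p then becomes 1 − (1 − p)^k in the survey. The range k = 0.5 to 2.0 is assumed, not taken from the document, and the two Study 005 percentages stand in for the unknown everolimus values.
- p = 4.8%: 2.4% at k = 0.5, 9.4% at k = 2.0.
- p = 12.6%: 6.5% at k = 0.5, 23.7% at k = 2.0.

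With no difference in risk, the survey could look better or worse than the reference, depending only on k.

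**The case against.** The strongest defence is that the protocol does not claim much for this comparison. It is qualitative, no test is done, differences in method and population will be reported with any other limitation on comparability, and 6.10 disclaims statistical comparison with earlier trials. The everolimus arm is named consistently in the synopsis, 5.1 and Part B, so the wider wording in 6.9.4 may only add context. Analysis detail is deferred to an SAP that is not shown, and person-time rates could be there.

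Most of this stands and limits the harm. It does not remove the defect. The disclaimers never mention observation time, and dropping a test does not make two unmatched percentages comparable. The protocol itself fixes the measure and gives the contrast an exploratory place, so an SAP would have to depart from the stated objective to repair it. Competing-risk methods and the MedDRA term list can properly be left to the SAP.

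Section 6.5.4 also says that most events of concern occurred within three months. That statement pools all safety concerns, and 6.3 projects far more anemia (325) than fracture (14). It says little about fracture, whose own median is 277.5 days.

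A reader might go further and infer three things that the document does not support:
- **That follow-up distorts the contrast as much as any drug effect.** This would need the everolimus figures, which are absent, and the bounds in Step 2 include a negligible effect.
- **That the cap flatters belzutifan.** The cap can only lower the survey's own percentage, but the net direction depends on everolimus exposure. If that was short, the survey could look worse.
- **That the risk management decision rests on this comparison.** Section 3 ties that review to the study's results as a whole.

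**Conclusion.** The point holds as a design weakness of moderate weight. Followed as written, the plan contrasts percentages gathered over different and variable observation times, so exposure time can create or conceal a difference. Neither the size nor the direction of the net bias can be stated from the protocol.

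The only available gauge is the effect of the cap on the Study 005 percentages in 6.3: a loss of 0.3 to 2.4 points for fracture and 0.3 to 6.2 points for hemorrhage. It rests on the assumption that the onset times and the 372 subjects belong together, and it is not an estimate of bias in the everolimus contrast. Separately, 5.1, 6.9.2 and 6.9.4 do not agree on where the contrast belongs or on its benchmark. The event window also differs: 5.1 speaks of events during administration, while 6.7.3 collects for a further 30 days.

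**What to change.** 1. In 6.9.2, add the descriptive contrast for hemorrhage and fracture, with the Study 005 everolimus arm as the named benchmark. Keep other studies in 6.9.4 as context only.
2. Restrict the Study 005 figures to the survey's window: first 52 weeks, on treatment plus 30 days. State the everolimus reference values and exposure.
3. On both sides, report exposure-adjusted incidence and/or 52-week cumulative incidence with 95% CIs, beside the crude percentages and without a test. The common window is not enough alone, because time on treatment within 52 weeks can still differ.
4. In 6.9.4 and 6.10, add length of follow-up and exposure to the limits on comparability.
5. Reconcile the event window in 5.1 with the post-treatment collection in 6.7.3.

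**Cost.** Wording changes, one re-cut of existing Study 005 data (assuming the sponsor holds the subject-level records) and a little more analysis. Section 6.6 already collects treatment start and stop dates and event onset dates, so the survey needs no new data.
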